#### **7.3.3.7 Chemosis**

It is defined as conjunctival edema, the result of an inflammatory reaction. It is classified as present or absent. The evaluator will use a narrow beam of light at 60° and measure whether the conjunctiva separates from the sclera in  $\geq 1/3$  of the total eyelid opening or if it exceeds the gray line. [47]

~~Handling as EA: Your presence will be considered as an EA.~~

## 7.4 Study visits and activities program

### 7.4.1 Description of activities per visit

The procedures are listed in the order in which they are suggested to be performed, trying to maintain the consistency of assessments and, as far as possible, from the least invasive to the most invasive.

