### 7.3.3.1 Adverse events

As defined in section 8.2, an AE is any unfavorable medical occurrence in a subject who is administer a PI, regardless of causal attribution.

The management of AEs will be carried out as described in the Adverse Events section.

The IP will record in the corresponding section of the electronic case report form (eCRF).

in English Case Report Form) the AEs that the subjects of the study may present in addition to referring to it in the medical record.

For an adequate evaluation of the EA, in addition to the directed questioning, it is necessary to carry out in each Visit the Comprehensive Ophthalmological Evaluation which consists of: the ophthalmological examination of the eyelids and annexes; anterior segment and posterior segment that is performed in a routine ophthalmological examination, whose procedures are not specifically included in the study variables. The evaluation of pole posterior may be with direct or indirect ophthalmoscopy, with or without pharmacological mydriasis, at the discretion of the IP.

An evaluation of the fundus will be performed to look for abnormalities that could alter the results of the study.

The IOP will be measured in this evaluation, with the instrument of the IP's choice, it should be measured after the evaluation of the stains. The result of the assessment will be recorded in the clinical record. In the eCRF only Findings that are considered as such by the IP will be reported as AEs.

According to the available literature, the expected AEs for the use of PI are: dysgeusia, eye irritation, Headache, nasopharyngitis, dry eye, ocular itching, nasal congestion and rhinorrhea.[42]

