#### **7.3.3.4 Corneal and conjunctival staining with fluorescein**

A drop of topical anesthetic will be instilled in the conjunctival fornix, then a drop will be applied. second drop on the tip of the fluorescein strip allowing it to sit on the strip for 5 seconds to elute the dye, shaking off the excess at the end. A small contact of the strip with the conjunctiva is made in the temporal fornix, while the patient looks up, without damaging the conjunctiva. It will be classified as according to the Oxford scale.[45]

The PI will record in the file and the eCRF the grade awarded for fluorescein staining of OD and OS respectively.

Management as AE: Corneal staining that is equal to or greater than grade III will be considered as AE.

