#### **7.3.3.5 Conjunctival staining with lissamine green**

After the fluorescein examination, a drop of lissamine green will be applied to the tip of the strip. saline solution allowing it to sit on the strip for 5 seconds to elute the dye. A drop of the strip in the temporal fornix, while the patient looks up, without damaging the conjunctiva. It can be ask the patient to blink repeatedly to avoid accumulation in the conjunctival folds. The scan should be performed between 1 and 4 minutes after instillation through a density filter. neutral or with the red-free filter. It will be graded according to the Oxford scale. [45]

The PI will record in the file and the eCRF the grade awarded for fluorescein staining of OD and OS respectively.

Management as AE: Corneal staining that is equal to or greater than grade III will be considered as AE.

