#### 7.4.1.1 Baseline Visit

- ~~Signature of the ICF~~: refers to the signing of the written informed consent document. Without informed consent, none of the study procedures can be performed.
- ~~Medical record~~: refers to the technical, clinical, and legal document that chronologically records the subject's health conditions, medical procedures, and other procedures performed on the subject. It includes anthropometric measurements, anamnesis, a comprehensive ophthalmological examination that allows determining the patient's eligibility, i.e., evaluation of both eyes and ocular adnexa, slit-lamp examination of the ocular surface and anterior segment, and fundoscopy. If the subject is taken from the study center's established population base, the existing medical record may be used; only one update is required.
- ~~Evaluation of concomitant medications~~: refers to the IP questioning the subject, inquiring about the use of medications.
- ~~Urine pregnancy test~~: This refers to a rapid pregnancy test performed on all women of childbearing age who wish to enter the study. By childbearing age, we mean women who have experienced menarche but have not yet experienced menopause. Menopause is defined as 12 months from the last menstrual period in women over 40 years of age, or who have undergone a hysterectomy or bilateral oophorectomy. Women of childbearing age using contraceptive methods, including bilateral tubal obstruction, must undergo a pregnancy test.

This test will be performed by the IP or designated team member according to the instructions on the device provided by the sponsor.

- ~~Vital signs~~: refers to heart rate, respiratory rate, systemic blood pressure, and temperature. This information must be recorded in the patient's medical history and progress notes. • ~~ccVA~~: See 7.3.3.2

---

- ~~ICQ~~: See 7.3.3.2
- ~~Ocular surface stains~~: See 7.3.3.4 and 7.3.3.5
- ~~Ophthalmological evaluation~~: See 7.3.3.1
- ~~Eligibility criteria~~: refers to the review by the PI, where it is confirmed that the subject can be included in the study by meeting the inclusion criteria and not meeting the exclusion criteria.

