- ~~PI Assignment~~: Refers to determining the intervention the patient will follow during the study. Since this is an open-label study, all eligible subjects will be assigned to PRO-172. However, assignment is the procedure by which the number of a given medication is linked to the subject's identification number. This assignment will be performed at the baseline visit (day 1).
- ~~Delivery of the PI and start of intervention~~: Refers to the delivery of the PI to the study patient by the research center.

- EA Assessment: See 7.3.3.1
- Delivery of patient materials and instructions for completion: This refers to the PI providing the subject with the subject's diary, identification card, and calendar, improving adherence. Staff assigned by the research center will provide the subject with prior training on how to complete the diary.

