#### 7.4.1.2 Final Visit

- § Evaluation of concomitant medications: See 7.5.1.1 above
- § Urine Pregnancy Test: See above 7.5.1.1
- § Vital signs: See 7.5.1.1 above
- § AVcc: See 7.3.3.2
- § Ocular surface stains: See 7.3.3.4 and 7.3.3.5
- § Comprehensive ophthalmologic evaluation: Ver7.3.3.1
- § EA Assessment: See 7.3.3.1
- § ICO: See 7.3.3.2
- § Subject Diary Assessment: See 7.5.1.1
- § Adhesion assessment: See 7.5.1.1
- § Return of PI and Subject Diary: Refers to the return by the subject of the PI and subject diary to the research center.

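### The label safe and tolerable rests only on unexpected related adverse events, so the primary comfort score (ICO) cannot affect it; a minor second point is that the ICO's listed place differs between the two visits

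*Protocol*

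**What the plan says.** **Tolerability and the rule.** Protocol 3.2 has two specific objectives: safety through unexpected adverse events related to the product, and tolerability through the ICO score. Protocol 7.3.1 and SAP 6.1 list both as primary variables. The ICO gets a within-group Wilcoxon test (Protocol 7.3.3 and 10.1.2; SAP Table 3 and 7.0). The hypotheses in the synopsis, Protocol 3.4.1 and SAP 3.0, and the closing sentence of Protocol 10.1.5, use one criterion for safe and tolerable together: unexpected related events in fewer than 10% of the study population. None of them mentions the ICO. Protocol 7.3.3.2 adds that an ICO score by itself is not to be treated as an adverse event.

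**Visit order.** Protocol 7.4.1 introduces its lists this way: "The procedures are listed in the order in which they are suggested to be performed, trying to maintain the consistency of assessments". It adds that they run, as far as possible, from less to more invasive. In 7.4.1.1 the ICO (printed as ICQ, with the ICO's cross-reference) stands between visual acuity and the stains. In 7.4.1.2 the entry "ICO: See 7.3.3.2" comes after the stains, the ophthalmological evaluation and the entry "EA Assessment: See 7.3.3.1". The staining procedure begins as follows: "A drop of topical anesthetic will be instilled in the conjunctival fornix". Lissamine green comes next: "After the fluorescein examination, a drop of lissamine green will be applied to the tip of the strip". Protocol 7.3.3.1 places the pressure measurement after the stains.

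**The concern.** A plan that names a measure for tolerability and then declares tolerability without it can reach a conclusion that its own primary data contradict. If comfort scores worsened clearly by day 8, 10.1.5 would still call the product tolerable provided few subjects had unexpected related events. Discomfort has little chance of entering by the adverse-event route. Besides the exclusion in 7.3.3.2, section 7.3.3.1 lists eye irritation, dry eye and ocular itching as expected, so events of those kinds do not count as unexpected on a plain reading. The ICO asks about dryness and itching directly.

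The order point is smaller. The study has no comparator, so day 8 against baseline is the only ICO contrast. Procedures that precede the questionnaire at one visit and not at the other could be mixed with a product effect.

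**Working it through.** **1. Can the ICO change the verdict?** Set the provisions side by side.

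- Protocol 3.2: tolerability is measured by the ICO.
- Protocol 10.1.5 and the three sets of hypotheses: the only input is the share of subjects with unexpected related events.
- Protocol 7.3.3.2: an ICO score alone is not such an event.
- Wilcoxon test of the ICO: planned at alpha 0.05, with no threshold and no link to the verdict.

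The verdict is therefore the same at every ICO value.

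**2. How many events does the rule allow?** The plan's sample size is 18 raised by 20%: 18 × 1.20 = 21.6, rounded up to 22. Its formula gives 18 with p = 0.30, p0 = 0.475, delta = 0.10, one-sided alpha 0.05 and power 80%: 0.30 × 0.70 × [(1.645 + 0.842)/(0.30 − 0.475 − 0.10)]² = 17.17, rounded up to 18. The documents do not say which rates are p and p0, so this assignment is an assumption. Nothing below depends on it.

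The denominator of the 10% rule is not fixed. In 10.1.5 the rule directly follows a restriction to subjects with adherence of at least 75%. In 10.1.3 safety covers everyone exposed. In 10.1.2 and SAP 7.0 adverse-event reporting covers all assigned participants. In 10.2.2 losses from 22 down to 18 are foreseen. Over that range:

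| Subjects counted | Largest passing count | First failing count |
|---|---|---|
| 22 | 2 (9.1%) | 3 (13.6%) |
| 21 | 2 (9.5%) | 3 (14.3%) |
| 20 | 1 (5.0%) | 2 (10.0%, not below 10%) |
| 19 | 1 (5.3%) | 2 (10.5%) |
| 18 | 1 (5.6%) | 2 (11.1%) |

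**3. Do the hypotheses agree?** Protocol 3.4.1 and the synopsis put H0 below 10% and H1 above 10%. SAP 3.0 puts both H0 and H1 below 10%, so as written its two hypotheses do not separate any outcomes.

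**4. Order of procedures.**

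- Baseline: visual acuity, ICO, stains, ophthalmological evaluation; adverse-event assessment later.
- Day 8: visual acuity, stains, ophthalmological evaluation (including pressure), adverse-event assessment, ICO.

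The anaesthetic drop, both dyes, the pressure measurement and the adverse-event questioning thus precede the ICO on day 8 only. The documents give no ICO standard deviation and no effect of these procedures on the score, so no size can be computed.

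**5. Check of the proposed interval.** With 22 pairs there are 22 × 23/2 = 253 Walsh averages. The 66th to 188th give exact coverage of 95.4% if there are no ties or zero changes. With 18 pairs there are 18 × 19/2 = 171, and the ranks become the 41st to 131st. The ranks must therefore follow the actual number of pairs. The ICO is a discrete score, so coverage is approximate when ties occur.

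**The case against.** **On the rule.** The ICO is a primary variable with its own test, so an unfavourable change would be tested and reported whatever 10.1.5 says. That stands. A reader might infer that the plan ignores comfort data; it does not. What remains is that a stated rule grants the word tolerable without consulting them. A reader might also take 0 to 2 events as the fixed allowance. That holds for 21 or 22 subjects, not for 18 to 20.

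**On the order.** The order is only suggested. The ICO asks about the past week, not the moment, which dampens any effect of a drop given minutes earlier. The least-to-most-invasive principle in 7.4.1 already favours giving the questionnaire first, so the day-8 entry may simply be misplaced. All of this stands and keeps the point minor. A reader might infer that the ICO contrast is biased in a known direction. The documents do not support that: they provide nothing from which a direction or size could be derived.

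A reader might also infer that the baseline ICO can follow a mydriatic. The earlier medical-record item includes "a comprehensive ophthalmological examination that allows determining the patient's eligibility" with fundoscopy, and 6.3 permits a mydriatic. But the discretion over mydriasis, "with or without pharmacological mydriasis, at the discretion of the IP", is written for the comprehensive ophthalmological evaluation, which is listed after the ICO at baseline. The medical-record item names no drop. A mydriatic before the ICO is therefore conjecture, though a sentence placing the ICO before any drop would rule it out.

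**Conclusion.** The point holds in two parts of unequal weight.

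The main part is a mismatch between an objective and a decision rule. The defect is confined to the word tolerable, and its reach is complete within that limit: at any ICO value the label is given with 0 to 2 events among 21 or 22 subjects, or 0 to 1 among 18 to 20. This assumes the rule is applied as the observed percentage, as 10.1.5 words it, and that between 18 and 22 subjects are counted. The change should be made, because a summary claim bypasses the measure chosen to support it. The identical direction of H0 and H1 in SAP 3.0 has to be corrected at the same time; otherwise the edited SAP would still contradict itself.

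The minor part is a correction to a list. It matters only if the suggested order is followed. Confidence overall is medium: the text is clear on both parts, but the practical consequence of the order is unknown.

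**What to change.** **Decision rule.**

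- In the synopsis, Protocol 3.4.1 and 10.1.5, and SAP 3.0, limit the under-10% criterion to safe.
- In SAP 3.0, also change H1 to more than 10%, as in Protocol 3.4.1.
- Report tolerability separately as the ICO change from baseline: the planned Wilcoxon test plus the Hodges-Lehmann median change with a 95% confidence interval, its ranks set by the actual number of pairs.
- Make no pass/fail claim of tolerability unless an ICO criterion is fixed before the first subject is enrolled.

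**Order.**

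- In 7.4.1.2, list the ICO directly after visual acuity and before the stains.
- State at both visits that the ICO is completed before any eye drop or dye.
- The schedule tables can stay as they are, since they do not claim to give an order.

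**Cost.** Seven statements are reworded (two each in the synopsis, 3.4.1 and SAP 3.0, one in 10.1.5: 2 + 2 + 2 + 1 = 7). One analysis line is added, one list line moved, and one sentence added at each of two visits. No procedure, visit or subject is added, and the sample size does not change. The downsides are a protocol and SAP amendment, with the committee review and regulatory authorisation described in Protocol 11.2, and a summary claim that may be less favourable than the present rule would give.

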#### 7.4.1.1 Baseline Visit

- ~~Signature of the ICF~~: refers to the signing of the written informed consent document. Without informed consent, none of the study procedures can be performed.
- ~~Medical record~~: refers to the technical, clinical, and legal document that chronologically records the subject's health conditions, medical procedures, and other procedures performed on the subject. It includes anthropometric measurements, anamnesis, a comprehensive ophthalmological examination that allows determining the patient's eligibility, i.e., evaluation of both eyes and ocular adnexa, slit-lamp examination of the ocular surface and anterior segment, and fundoscopy. If the subject is taken from the study center's established population base, the existing medical record may be used; only one update is required.
- ~~Evaluation of concomitant medications~~: refers to the IP questioning the subject, inquiring about the use of medications.
- ~~Urine pregnancy test~~: This refers to a rapid pregnancy test performed on all women of childbearing age who wish to enter the study. By childbearing age, we mean women who have experienced menarche but have not yet experienced menopause. Menopause is defined as 12 months from the last menstrual period in women over 40 years of age, or who have undergone a hysterectomy or bilateral oophorectomy. Women of childbearing age using contraceptive methods, including bilateral tubal obstruction, must undergo a pregnancy test.

This test will be performed by the IP or designated team member according to the instructions on the device provided by the sponsor.

- ~~Vital signs~~: refers to heart rate, respiratory rate, systemic blood pressure, and temperature. This information must be recorded in the patient's medical history and progress notes. • ~~ccVA~~: See 7.3.3.2

---

- ~~ICQ~~: See 7.3.3.2
- ~~Ocular surface stains~~: See 7.3.3.4 and 7.3.3.5
- ~~Ophthalmological evaluation~~: See 7.3.3.1
- ~~Eligibility criteria~~: refers to the review by the PI, where it is confirmed that the subject can be included in the study by meeting the inclusion criteria and not meeting the exclusion criteria.
- ~~PI Assignment~~: Refers to determining the intervention the patient will follow during the study. Since this is an open-label study, all eligible subjects will be assigned to PRO-172. However, assignment is the procedure by which the number of a given medication is linked to the subject's identification number. This assignment will be performed at the baseline visit (day 1).
- ~~Delivery of the PI and start of intervention~~: Refers to the delivery of the PI to the study patient by the research center.

- EA Assessment: See 7.3.3.1
- Delivery of patient materials and instructions for completion: This refers to the PI providing the subject with the subject's diary, identification card, and calendar, improving adherence. Staff assigned by the research center will provide the subject with prior training on how to complete the diary.

#### 7.4.1.2 Final Visit

- § Evaluation of concomitant medications: See 7.5.1.1 above
- § Urine Pregnancy Test: See above 7.5.1.1
- § Vital signs: See 7.5.1.1 above
- § AVcc: See 7.3.3.2
- § Ocular surface stains: See 7.3.3.4 and 7.3.3.5
- § Comprehensive ophthalmologic evaluation: Ver7.3.3.1
- § EA Assessment: See 7.3.3.1
- § ICO: See 7.3.3.2
- § Subject Diary Assessment: See 7.5.1.1
- § Adhesion assessment: See 7.5.1.1
- § Return of PI and Subject Diary: Refers to the return by the subject of the PI and subject diary to the research center.

#### 7.4.2 Unscheduled follow-up visits

At the request of the patient or any other individual related to the study, visits may be carried out unscheduled follow-up visits for reporting adverse events. During these visits, the following must be collected all relevant data on reported adverse events and, where appropriate, establish an appropriate management plan.

### 7.5 Data collection

#### 7.5.1 Source documents

Source documents are all written or printed records derived from automated processes (for example, example: printouts of laboratory results issued by automated analysis equipment) where information is recorded for the first time and becomes part of the permanent records of the history of the patient. Examples of source documents include medical records, clinical progress notes, and reports, laboratory reports, office study reports, nursing notes, follow-up notes, surgical records, etc.

The IP is obliged to accept the monitoring of information related to the study, audits, review by part of ethics and research committees, and inspections by the health authority, this obligation involves direct access to source documents.

### 7.5.2 Electronic forms of data collection

All data relating to the protocol will be captured via an eCRF by team personnel. of research. Data relating to the protocol should NOT be captured directly in the eCRF, but which must be transcribed from the corresponding source document. This procedure allows the Carrying out monitoring to verify the information captured in the eCRF. It is the responsibility of the researcher that the information is transcribed to the eCRF in a correct, complete and timely manner. understands that all eCRF forms captured and submitted for data analysis are approved by the Researcher.

### 7.5.3 File

The data collected in this database is anonymous (it only stores the number of the patient along with other information of interest). The program used for the capture and storage of data covers the traceability requirements necessary for the execution of clinical studies. The data collected will be stored by the sponsor or designated clinical research organization for This and its storage will last for 10 years. The records of patient number assignment They will remain in the participating institutions under the care of the IP or his/her work team and must be protected for at least 5 years.

### 7.5.4 Unscheduled follow-up visits

At the request of the patient or any other individual related to the study, visits may be carried out unscheduled follow-up visits for reporting adverse events. During these visits, the following must be Collect all relevant data on reported adverse events and, where appropriate, establish an appropriate management plan.

## 8. Event evaluation and management adverse

---

### 8.1 Regulation and standards on adverse events

The registration and reporting of adverse events will be carried out in accordance with the guidelines established in the NOM-220-SSA1-2016 which is in accordance with the international ICH E6 guidelines.

### 8.2 Definition of adverse event

According to the International Conference on Harmonization (ICH), an adverse event (AE) is any adverse medical occurrence in a patient undergoing clinical research who is administered a product by a pharmacist, regardless of causal attribution.

Therefore, an AE can be any of the following: any undesirable medical event that is temporally related to the use of a medical product, whether or not it is considered to be related to said product; any new disease or exacerbation of an existing disease (worsening the nature, frequency, or severity of a known condition); relapse of a medical condition Intermittent (e.g., headache) not present at baseline; some deterioration in a laboratory value or other clinical test (e.g., electrocardiogram [ECG], X-ray) that is related to the symptoms or that produce a change in the study treatment or concomitant treatment or discontinuation of the study drug.

